1 PROTOCOL SUMMARY

1.1 SYNOPSIS

Title: The Role of Regional Anesthesia to Reduce Opioid Requirements Following Functional Endoscopic Sinus Surgery (FESS)

Study Description: Opioid analgesics are prescribed for moderate to severe pain disorders, however there are contraindications and side effects that are common to all opioids. We hypothesize using local regional anesthetic during sinus surgery will reduce pain, therefore decreasing the need for post-operative opioid medication. The primary objective is to determine if a long-acting regional anesthetic applied during a surgery will reduce post-operative oral opioid usage.

Objectives: *Primary Objective:* The primary objective is to determine if a long-acting regional anesthetic applied after a surgery will reduce post-operative oral opioid usage.

Secondary Objective: The secondary objective is to measure the level of each patient's pain.

Endpoints:

- *Primary Endpoint:* The amount of post-operative pain after FESS. Participants will self-report a pain score on a scale of 0-10, with 0 being "no pain" and 10 being "worst pain imaginable" on the provided questionnaire (see Appendix 1).

- *Secondary Endpoint:* Patient's daily pain medication usage. The amount of opioid medication used post-procedure will be determined by a pill count at the first post-operative clinic visit.

Study Population: It is anticipated that 30 subjects will be enrolled in this protocol. Potential subjects will be male or female adults over the age of 18 from the United States who undergo functional endoscopic sinus surgery under the supervision of one surgeon.

Phase: 4

Description of Study	Treatment group: 20 mL of 1.3% bupivacaine with 2 mg dexamethasone injected locally in the location for sensory nerves of the sinus cavities and face during the FESS.
Intervention:	Control group: No long-acting regional anesthetic will be used during the FESS.
Study Duration:	12 months
Participant Duration:	Up to 21 days (dependent on standard of care scheduling for first post-operative clinic visit)

1.2 SCHEDULE OF ACTIVITIES (SOA)

Procedures	Screening/ Baseline	Day of Surgery	Day 10-21
Informed consent	X		
Demographics	X		
Medical history	X		
Physical exam	X		
Vital signs	X		
Height & weight	X		
Nasal endoscopy	X		X
CT scans	X		
Randomization		X	
Administer study intervention		X	
Concomitant medication review	X	X	X
Adverse event review and evaluation	X	X	X
Pain diary		X	X
Visual analog scale	X	X	X
Pain medication reconciliation			X

2 INTRODUCTION

2.1 STUDY RATIONALE

Opioid analgesics are still being prescribed to help control moderate to severe pain, however these medications are not without risks. Patients are at an increased risk of dependence which is a growing national concern. We plan to conduct a clinical trial to evaluate the use of regional anesthesia after routine sinus surgery to help decrease the need for post-operative opioid use.

2.2 BACKGROUND

Opioid analgesics are prescribed for moderate to severe acute pain; however, there are contraindications, cautions, and side effects that are common with all opioids. Dependence and tolerance are also likely with regular opioid use, resulting in the current nationwide opioid epidemic. In

Alabama alone, there were 343 opioid-related overdose deaths in 2016, 124 of which were related to prescription opioids. Alabama providers have the highest prescribing rate in the country, nearly twice the national rate, per the NIH/NIDA website (<https://www.drugabuse.gov/drugs-abuse/opioids/opioid-summaries-by-state/alabama-opioid-summary>). In 2015, the Centers for Disease Control (CDC) released prescribing guidelines relating to chronic pain, and in 2018 Alabama's Blue Cross/Blue Shield insurance group limited the supply of opioids allowed to their members to 7 days (https://www.al.com/news/index.ssf/2018/03/bluecross_blueShield_changing.html).

There is currently no clinical guideline for prescribing post-operative opioid medications for functional endoscopic sinus surgery (FESS). A 2018 survey documenting prescribing patterns by 168 members of the American Rhinologic Society found that most physicians who participated prescribed, on average, 27 opioid pain pills for patients after surgery. Prior studies have been performed to help decrease the pain patient's feel after sinus surgery. Haytoglu (2016) revealed that adding non absorbable sinus packs loaded with local anesthetics such as bupivacaine achieved less pain values and improved patient satisfaction scores.

Given this current data we believe injecting patients with a long acting analgesic during the procedure will help reduce post-operative pain. If we can decrease the amount of pain patients have in the post-operative period we can theoretically decrease the number of opioid pain pills prescribed. We plan to also track the number of opioid pills consumed by patients in the post-operative period to obtain a somewhat uniform prescribing pattern within surgeons.

2.3 RISK/BENEFIT ASSESSMENT

2.3.1 KNOWN POTENTIAL RISKS

All of the drugs to be used in this study are FDA-approved, commonly-used, widely available, generic medications. These drugs will be prescribed at their standard dosing for their approved indications.

As outlined in the package inserts for the medications under study in this protocol, the following adverse reactions have been identified during post approval use. Because these reactions are reported voluntarily from a population of uncertain size, it is not always possible to reliably estimate their frequency or establish a causal relationship to drug exposure.

- *Risks associated with bupivacaine hydrochloride (MarcaineTM):* The most frequently reported adverse reactions are restlessness, anxiety, dizziness, tinnitus, blurred vision, tremors, nausea, vomiting, chills, and constriction of pupils (central nervous system reactions) and depression of the myocardium, decreased cardiac output, heartblock, hypotension, bradycardia, ventricular arrhythmias, including ventricular tachycardia and ventricular fibrillation, and cardiac arrest (cardiovascular system reactions). Other reported reactions include persistent anesthesia, paresthesia, weakness, or paralysis. Allergic reactions are characterized by signs such as urticaria, pruritus, erythema, angioneurotic edema (including laryngeal edema), tachycardia, sneezing, nausea, vomiting, dizziness, syncope, excessive sweating, elevated temperature, and possibly, anaphylactoid-like symptomatology (including severe hypotension). Reactions to MARCAINE are characteristic of those associated with other amide-type local anesthetics. A major cause of adverse reactions to this group of drugs is excessive plasma levels, which may be due to overdosage, unintentional intravascular injection, or slow metabolic degradation. In

addition to systemic dose-related toxicity, unintentional subarachnoid injection of drug during the intended performance of caudal or lumbar epidural block or nerve blocks near the vertebral column (especially in the head and neck region) may result in underventilation or apnea ("Total or High Spinal"). Also, hypotension due to loss of sympathetic tone and respiratory paralysis or underventilation due to cephalad extension of the motor level of anesthesia may occur. This may lead to secondary cardiac arrest if untreated. Patients over 65 years, particularly those with hypertension, may be at increased risk for experiencing the hypotensive effects of bupivacaine hydrochloride. Factors influencing plasma protein binding, such as acidosis, systemic diseases which alter protein production, or competition of other drugs for protein binding sites, may diminish individual tolerance. Bupivacaine hydrochloride carries a black box warning for cardiac arrest with difficult resuscitation or death during use for epidural anesthesia in obstetrical patients.

- *Risks associated with dexamethasone sodium phosphate injection:* The most frequently reported adverse reactions are anaphylaxis, infection, seizures, hypertension, erythema, rash, urticarial, nausea, vomiting, edema, petechial, ecchymosis, skin pigmentation abnormality, acne, headache, dizziness, vertigo, insomnia, anxiety, and depression.
- *Risks associated with protocol-mandated procedures:*
 - *Surgical procedures:* All surgical procedures will be performed in the routine manner. There will be no additional clinical or surgical risks, other than the normal risks for patients undergoing this type of treatment.
 - *Questionnaires:* Completion of a questionnaire and the questions might make the subject feel uncomfortable or upset. Subjects will have the choice to not answer any such questions.

2.3.2 KNOWN POTENTIAL BENEFITS

An article published in 2015 by Knezevic evaluated 14 studies in which physicians added dexamethasone into the local anesthetic used for brachial plexus block. They concluded patients injected with local anesthetic plus dexamethasone had improved post-operative pain when compared to a control group. Our goal is to apply this to sinus surgery in providing analgesia to the sensory nerves of the face/sinus. The immediate potential benefit for the patient is reduced discomfort and pain in the post-operative period. Potential long term benefits would include decrease need for post-operative opioid consumption therefore potentially decreasing the possible addictive habit of using opioids.

2.3.3 ASSESSMENT OF POTENTIAL RISKS AND BENEFITS

Routinely dexamethasone is used for general anesthesia to help decrease inflammation and post-operative swelling. All patients will be screened for any previous reactions to the medications being used in our study. Patient medical records will also be reviewed for past drug allergies. As our study plans to evaluate the local effects of bupivacaine with dexamethasone, we anticipate only mild local reactions, as we will not systemically inject the drugs being used. The risks to participants will likely encounter only local skin reactions to the medications. The information gained will help to possibly standardize how we treat post-operative pain after sinus surgery.

3 OBJECTIVES AND ENDPOINTS

OBJECTIVES	ENDPOINTS	JUSTIFICATION FOR ENDPOINTS
Primary	Primary	Primary
The primary objective is to determine if a long-acting regional anesthetic applied after a surgery will reduce post-operative oral opioid usage.	The amount of post-operative pain after FESS. Participants will self-report a pain score on a scale of 0-10, with 0 being “no pain” and 10 being “worst pain imaginable.”	The use of narcotics post-operatively is to control pain; if we can reduce post-operative pain, essentially we can decrease post-operative opioid use.
Secondary	Secondary	Secondary
The secondary objective is to measure the level of each patient's pain.	Patients' daily pain medication usage. The amount of opioid medication used post-procedure will be determined by a pill count at the first post-operative clinic visit.	Pain is a subjectively based outcome that can be difficult to determine prior to a surgery. We believe if we are able to reduce pain in the majority of our patients tested then, we can apply this on a global scale to create a uniform number of opioid pain medications prescribed after surgery.

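### The primary objective is opioid use but the primary endpoint is pain, so the primary result would not by itself answer the primary objective (Protocol 1.1, 3 and 4.1)

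*Protocol*

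**What the plan says.** Section 3 of the Protocol lists objectives, endpoints and justifications side by side.

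- **Primary row.** The objective is: "The primary objective is to determine if a long-acting regional anesthetic applied after a surgery will reduce post-operative oral opioid usage". The endpoint is "The amount of post-operative pain after FESS", and Section 1.1 gives the measure: "Participants will self-report a pain score on a scale of 0-10". The justification is that "if we can reduce post-operative pain, essentially we can decrease post-operative opioid use".
- **Secondary row.** The objective is each patient's level of pain. The endpoint is daily pain medication use, with this measure: "The amount of opioid medication used post-procedure will be determined by a pill count at the first post-operative clinic visit". The justification speaks of reducing pain in most patients so as to "create a uniform number of opioid pain medications prescribed after surgery".

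Section 1.1 puts the hypothesis as a chain: local anesthetic during surgery "will reduce pain, therefore decreasing the need for post-operative opioid medication". Section 4.1 repeats that hypothesis in similar words. The trial title and Section 2.1 both present lower opioid need as the purpose. Under Section 4.1, participants keep a diary for 10 days after surgery, recording pain, opioids and over-the-counter analgesics each day. Remaining pills are counted at the first post-operative visit.

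**The concern.** The primary endpoint carries a trial's main conclusion, so it should measure what the primary objective asks. Here the objective asks about opioid use, and the endpoint measures something earlier in the hypothesised chain. Followed as written, the comparison of 15 with 15 participants says whether reported pain differed.

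Two misreadings could follow. Lower pain could be reported as meeting an opioid-reduction objective that was not tested as primary. Or a null pain result could be read as failure although opioid use had fallen.

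**Working it through.** No figure in the plan needs reproducing, so the check sets the sections side by side.

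| Section | Primary objective | Primary endpoint | Secondary objective | Secondary endpoint |
|---|---|---|---|---|
| 1.1 | Less oral opioid use | Pain, 0-10 | Pain level | Daily pain medication use; opioids by pill count |
| 3 | Less oral opioid use | Pain, 0-10 | Pain level | Daily pain medication use; opioids by pill count |
| 4.1 | Less oral opioid use | Pain, 0-10 | Pain level | Daily pain medication use |

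The pairing is the same each time, so it is not an isolated slip in one section.

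**Does the stated rationale close the gap?** The Section 3 justification takes the step from less pain to less opioid use as its premise. Sections 1.1 and 4.1 present that same step as part of what the trial hypothesises. A premise that the trial itself puts forward as a hypothesis cannot turn a pain result into an opioid result.

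**Can the two outcomes separate?** Pain and drug use are recorded daily over the same 10 days (Section 4.1), and Section 3 says that narcotics are taken to control pain. There are four possible combinations:

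1. Pain lower, opioid use lower: the primary endpoint and the primary objective agree.
2. Pain similar, opioid use similar: they agree.
3. Pain similar, opioid use lower in the treated group, for example because controls took more analgesics until their pain was comparable: the primary endpoint is null, yet the objective is met.
4. Pain lower, opioid use similar: the primary endpoint is favourable, yet the objective is not met.

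In cases 3 and 4 the primary result points the wrong way for the primary objective. The documents do not say how likely these cases are.

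**Is opioid use ready to serve as primary?** It is collected, but from two sources over different periods.

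- The diary covers 10 days (Section 4.1).
- The pill count is taken at a visit on Day 10-21 (Sections 1.2 and 8.1), or on Post-Op Day 14 (Section 6.3).
- With both counted from surgery, the pill count can cover 14 − 10 = 4 days beyond the diary, or up to 21 − 10 = 11 days. Pills taken in those days would look like disagreement between the sources.

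**Is pain ready to serve as primary?** The endpoint scale is 0-10 in Sections 1.1, 3 and 4.1, but the diary described in Section 4.1 uses 1-10. The diary as described has no entry for zero.

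**The case against.** The strongest defence is that pain was chosen deliberately. Section 3 gives a reason for it, and Sections 1.1 and 4.1 set out the chain from block to pain to opioid need. Opioid use is a named secondary endpoint with its own pill count. The trial enrols 30 people, and the title at the end of the document calls it a pilot study. Both outcomes are planned, so the opioid question is not lost.

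Much of this stands. It rules out several stronger readings that a reader might infer:

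- *The pairs were transposed by mistake.* The explicit justification for pain as primary does not fit that reading.
- *The trial cannot answer its opioid question.* It can, through the secondary endpoint.
- *The protocol treats the pain-to-opioid link as established throughout.* Sections 1.1 and 4.1 call it a hypothesis. Section 2.2 calls a related step theoretical, but that step concerns pills prescribed, not pills used. Only the Section 3 justification is worded almost flatly.
- *The cited background literature contains no opioid evidence.* The protocol summarises each source in a sentence or so, and the sources are not at hand.

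None of this removes the mismatch. A deliberate rationale explains why pain was chosen, but it does not make a pain result an answer about opioid use. Pilot status lowers the stakes, but a pilot's primary result should still address its stated objective. Objectives and endpoints are fixed in the protocol, so a separate SAP could not resolve a conflict within these sections.

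**Conclusion.** The point holds. In Sections 1.1, 3 and 4.1 the primary endpoint does not measure the primary objective, and the secondary pair is crossed in the opposite direction. The primary result on pain would not by itself show whether opioid use fell, and only a secondary endpoint addresses that.

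The conclusion rests on the text alone and needs no assumed effect size, variance or correlation. A reader might want to say how often, or by how much, the pain and opioid results would disagree, or what power the trial has for each. The documents give nothing from which to derive that, so no such figure is offered.

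**What to change.** Before outcome data are examined, align the pairs in Sections 1.1, 3 and 4.1 in one of two ways.

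**(a) Make opioid use primary.** Post-operative oral opioid consumption becomes the primary endpoint and pain the secondary endpoint, which then matches the secondary objective as it stands. Name one source and one fixed period. If the 10-day diary is chosen, say that it replaces the pill count as the stated measure, and compare the count with the diary only over the same period. Reconcile the Day 10-21 and Day 14 descriptions of the visit. Also state the risk acknowledged in Section 4.2, that controls who notice intact facial sensation may use more opioids.

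**(b) Keep pain primary.** Restate the primary objective as pain reduction and make opioid use the secondary objective. Limit any opioid-sparing claim to a secondary result. Reconcile the 1-10 diary scale with the 0-10 endpoint scale.

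Under either option, word the pain-to-opioid link in Section 3 as a hypothesis, as Sections 1.1 and 4.1 already do.

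**Cost.** No new data or visit is needed: the diary, the pill count and their reconciliation are already planned (Sections 4.1 and 6.3). Either option needs an amendment with ethics board approval, and any separate SAP must follow it. Option (b) is mostly rewording plus the scale correction. Option (a) goes further if the diary replaces the pill count, because it then changes the stated measure, and it makes primary the outcome that Section 4.2 expects to be affected when controls notice intact sensation. Pain is self-reported, so (b) may not fully avoid that risk.

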4 STUDY DESIGN

4.1 OVERALL DESIGN

Opioid analgesics are prescribed for moderate to severe pain disorders; however, there are contraindications and side effects that are common to all opioids. We hypothesize using local regional anesthetic after sinus surgery will reduce pain, therefore decreasing the need for post-operative opioid consumption.

This is a Phase 4, randomized, single-blinded, single-site, parallel-assignment intervention with a primary purpose of supportive care after functional endoscopic sinus surgery (FESS). It is anticipated that 30 subjects will be enrolled in this protocol. Potential subjects will be male or female adults over the age of 18 from the United States who undergo functional endoscopic sinus surgery (FESS) under the supervision of one surgeon.

Potential participants will be approached during their regularly-scheduled clinic visit about participation in the study. If they agree to participate, they will sign an informed consent form. During the baseline visit, demographic information, medical history, concomitant medications, vital signs, height, and weight will be collected. A routine nasal endoscopy will be performed to assess the need for surgical intervention, and routine CT sinus scans will be obtained and/or reviewed.

Participants will be randomized to one of the two following groups:

- **Treatment Group (n = 15):** participants will receive 20 mL of 1.3% bupivacaine with 2 mg dexamethasone injected locally in the location for sensory nerves of the sinus cavities and face during the FESS procedure
- **Control Group (n = 15):** participants will not receive regional anesthetic during the FESS procedure

Participants will have their scheduled functional endoscopic sinus surgery procedure. After surgery, participants will be given a pain diary to record their pain score on a scale of 1-10, and a place to record their use of opioids, as well as over-the-counter non-steroid anti-inflammatories such as acetaminophen and ibuprofen. Participants will record their scores and drug use daily for 10 days post-surgery. At their first post-operative clinic visit, the diary will be reviewed, and their opioid use will also be evaluated by counting the pills left on their prescription.

Data points/variables to be collected during the study could include the following, to be ascertained from the medical record and/or patient report:

- Name
- Medical Record Number
- Age
- Gender
- Type of surgery
- Duration of surgery
- Medications given by anesthesia intra- and post-operatively
- Post-operative pain medication used prior to and after discharge
- Post-operative complications
- Post-discharge/post-operative pain evaluation by patient diary

Participant duration will be up to 21 days, dependent on standard-of-care scheduling of the first post-operative clinic visit. It is anticipated that the study will be open to enrollment for 12 months.

Primary Objective: The primary objective is to determine if a long-acting local regional anesthetic applied after a surgery will reduce post-operative oral opioid usage.

- Primary Endpoint: The amount of post-operative pain after FESS, as determined by patient self-report of pain on a scale of 0-10.

Secondary Objective: The secondary objective is to measure the level of each patient's pain.

- Secondary Endpoint: Patient's daily pain medication usage.

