8 STUDY ASSESSMENTS AND PROCEDURES

8.1 STUDY ASSESSMENTS

Subjects over the age of 18 who are undergoing functional endoscopic sinus surgery for chronic sinusitis as part of routine clinical care will be approached to participate in the study. Subjects screened and enrolled will follow the schedule of events provided in Section 1.2. The following evaluations will be performed:

Screening/Baseline:

- Obtain written informed consent
- Obtain demographic information
- Obtain medical history
- Obtain concomitant medication information
- Obtain routine vital signs, including height and weight
- Obtain routine nasal endoscopy
- Obtain/review routine CT scans of the sinus. This information may be obtained through review of existing data

Day of Surgery

- Randomization into the Treatment Group or the Control Group, as per measures outlined in Section 6.2
- Scheduled routine surgical procedure previously planned, based on subject's condition
- Study intervention administration to all subjects
- Post-operative medication diary will be given to all subjects
- Post-operative visual analog pain scale will be given to all subjects
- Assessment of adverse events
- Assessment of concomitant medications

Post-Operative Clinic Visit #1 (Day 10-21)

- Obtain routine nasal endoscopy
- Review of medication diary
- Review of visual analog pain scale
- Pain medication reconciliation via pill count

- Assessment of adverse events
- Assessment of concomitant medication

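### Section 4.1 scores the daily pain diary 1-10 while the primary endpoint is pain on 0-10, and no section says which form supplies that endpoint

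*Protocol*

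**What the plan says.** The protocol gives a pain-score range in four places.

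- The synopsis (1.1) and Section 3 define the primary endpoint. Section 3 reads "Participants will self-report a pain score on a scale of 0-10", and both sections anchor 0 as no pain and 10 as the worst imaginable.
- The end of Section 4.1 repeats the endpoint, "as determined by patient self-report of pain on a scale of 0-10", without anchors.
- Earlier in Section 4.1, the design description says "participants will be given a pain diary to record their pain score on a scale of 1-10". It gives no anchors, and continues: "Participants will record their scores and drug use daily for 10 days post-surgery".

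The form that collects pain is named in several ways.

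- The synopsis places the 0-10 score "on the provided questionnaire (see Appendix 1".
- The data list in Section 4.1 has "Post-discharge/post-operative pain evaluation by patient diary".
- The Schedule of Activities (1.2) has a pain diary row and a separate row, "Visual analog scale". Only the latter is marked at Screening/Baseline.
- Section 8.1 says "Post-operative visual analog pain scale will be given to all subjects" and, as a separate item, hands out a medication diary.
- Section 6.3 describes a medication diary for dates and times of pain medication and mentions no pain score.

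**The concern.** The two ranges differ at the one value that the endpoint defines as no pain. Section 4.1 makes the diary a stated source of post-operative pain data and describes the only daily pain-score recording in the protocol, so the diary is a serious candidate for the source of the primary endpoint. If it is the source and the printed form follows the 1-10 wording, a participant without pain has no defined value to enter. A recorded 1 may then mean either no pain or slight pain, and the scores are not on the scale that the endpoint names.

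An analysis plan could not repair this afterwards. The range is fixed when the form is printed and completed, and a form without 0 leaves nothing from which to separate the two meanings of 1. The treatment is meant to reduce pain, so pain-free scores may be more frequent in the treated arm. Any distortion at the bottom of the scale would then fall unequally on the two arms.

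**Working it through.** **Text check.** Three of the four range statements say 0-10 and one says 1-10. The odd one and one of the three stand in the same section, so Section 4.1 contradicts itself as well as the synopsis and Section 3. In whole numbers, 0-10 has 11 levels and 1-10 has 10; the missing level is the anchored 0. No section equates the questionnaire, the diary and the visual analog scale, or says which of them supplies the endpoint.

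**Size, on condition that the diary supplies the endpoint and its form has no 0.** The documents give no means, SDs or pain-free shares, so all of these are assumed. Each arm has a normal latent score, rounded to whole numbers and clipped to 0-10. The latent benefit is 1 point, with control/treated means of 6/5, 5/4, 4/3, 3/2 and 2/1, and the SD is 1.5 to 2.5.

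Let D be the control mean minus the treated mean on 0-10, and let z_C and z_T be the shares of zeros in each arm. The standardized effect is the difference divided by the root of the average of the two arm variances.

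- Zeros written as 0 anyway: D is unchanged.
- Every zero written as 1: D' = D − (z_T − z_C).
- Half of the zeros written as 1: D' = D − (z_T − z_C)/2.
- Zeros left blank and dropped: each arm mean is divided by (1 − z) before differencing.
- 1 used as the no-pain end, with the rest compressed linearly: score = 1 + 0.9 × (0-10 score), so D' = 0.9 × D. The SDs shrink by the same factor (ignoring rounding), so the standardized effect does not change.

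**Worked example, SD 2, means 3/2.** z_C = 0.1056, z_T = 0.2266, D = 0.8943, standardized effect 0.487.

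- All as 1: 0.8943 − 0.1210 = 0.7733, which is 13.5% smaller; standardized 0.471, 3.3% smaller.
- Half as 1: 0.8943 − 0.0605 = 0.8338, 6.8% smaller; standardized 0.478, 1.8% smaller.
- Blank: 3.0558/0.8944 − 2.1616/0.7734 = 0.622, 30.5% smaller; standardized 0.390, 19.9% smaller.
- Linear compression: 0.9 × 0.8943 = 0.805, 10% smaller; standardized still 0.487.

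**Raw shrinkage at SD 2 across the assumed means**

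| Means | All as 1 | Half as 1 | Blank |
|---|---|---|---|
| 6/5 | 0.9% | 0.5% | 4.5% |
| 5/4 | 2.8% | 1.4% | 10.7% |
| 4/3 | 6.8% | 3.4% | 20.2% |
| 3/2 | 13.5% | 6.8% | 30.5% |
| 2/1 | 22.6% | 11.3% | 38.4% |

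**Range over SD 1.5 to 2.5**

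| Handling of pain-free days | Raw shrinkage | Standardized loss |
|---|---|---|
| Written as 0 | 0% | 0% |
| All as 1 | 0.1% to 25.1% | 0% to 7.8% |
| Half as 1 | 0.1% to 12.5% | 0% to 4.7% |
| 1 as the no-pain end, linear | 10% | 0% |
| Blank and dropped | 0.6% to 38.7% | 0.2% to about 28% |

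In points, the all-as-1 case loses between 0.001 and 0.21.

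**The case against.** The strongest reply is that the 1-10 wording may never touch the primary endpoint. The only place that ties the endpoint to a form is the synopsis, and that form is a questionnaire scored 0-10 with both anchors. Section 8.1 gives pain to the visual analog scale and calls the diary a medication diary, as does Section 6.3. The line in Section 4.1 that names the diary as a source of pain data belongs to a list of variables that could be collected, not a firm specification. Since three of four statements say 0-10, a slip in one digit is the likeliest explanation. Appendix 1 is not in the text at hand and may settle both the range and the identity of the form.

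Much of this stands. A reader might infer that Section 4.1 sets the collection rule for the primary endpoint, and so that the trial's result would be biased. The documents do not support that: they leave the source instrument open, and the form could carry 0. Nor is the absence of Appendix 1 from the text at hand a fault in the plan. It is also fair that the percentages rest wholly on assumed values, and that not every response pattern does harm. If both arms treat 1 as the no-pain end, the comparison remains valid and only its scale changes.

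The contradiction itself survives. The protocol gives no basis for setting the 1-10 wording aside as belonging to a secondary form, and staff preparing the diary from Section 4.1 would print a scale that the endpoint definition does not allow.

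**Conclusion.** The inconsistency is certain and should be corrected: the diary range in Section 4.1 conflicts with the primary endpoint as defined in the synopsis, in Section 3 and later in Section 4.1 itself. The source instrument is also left unidentified.

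The numerical consequence is conditional on two things that the documents do not establish: that the diary supplies the endpoint, and that its form lacks 0. If both hold, the effect on the raw difference runs from none to about 25% where zeros stay 0 or become 1, and is 10% where the scale is compressed. The standardized loss in these cases is at most about 8%, so the damage is mainly to the reported difference and its scale, not to power. The larger figures, up to about 39% raw, need scores near zero and every pain-free day left blank and dropped, which missing-data handling in an analysis plan could address. If the form already carries 0-10, what remains is a contradictory protocol and no distortion of data.

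**What to change.** - In Section 4.1, change the diary scale to 0-10 and give the Section 3 anchors for both ends.
- Check that the form handed to participants offers 0.
- In Sections 1.1, 1.2, 4.1 and 8.1, use one set of names and state whether the Appendix 1 questionnaire, the pain diary and the visual analog scale are the same form. If they are not, state which single one supplies the primary endpoint.

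The cost is wording edits in four sections and one check of the form. No visits, participants or assessments are added.
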